During the first six months of the study, a member of the clinic social work team, on behalf of the patients, will manage monthly vouchers of \$650 that can be used for temporary housing options from a list compiled by the study. These vouchers will be dispensed at the beginning of the month, and member of the clinic social work team will ensure these are used solely for housing purposes. The participants will meet with the member of the clinic social work team at least once a month for twelve months. These meetings could be scheduled as frequently as several times a week depending on the issues needing to be addressed for the participants. Social work assistance is already available to patients at the Addiction Treatment Program, but the social work assistance offered in this study would be more intensive and tailored specifically to the needs of the study participants. Because these meetings would address issues that would keep participants housed after the study ends, participants will be encouraged to schedule these meetings more frequently than once a month.

The goal of these meetings would be to ensure participants remain housed after the housing vouchers and study ends. The meetings could accomplish this goal in several ways. The member of the clinic social work team would conduct a needs assessment on the participants to determine barriers to stable housing and the sources of income are already available to the participant. A member of the clinic social work team could help participants obtain benefits for which they are eligible like Social Security Income. Participants could also take part in employment-training services that would allow them to be hired for jobs and gain income. Once the participants are housed, member of the clinic social work team could address issues placing them at risk for losing their housing such as resolving disputes with their landlords or teaching the participants budgeting strategies to manage their income and rent. The member of the clinic social work team would help the participants apply for permanent housing vouchers from the city of Baltimore so that the participants remain housed once the study is over. Attending meetings with the member of the clinic social work team will be required for the housing vouchers to be used on behalf of the participant, and participants will be removed from the study if they miss more than 50 percent of scheduled meetings with the member of the clinic social work team.

It is hypothesized that the stability provided by the housing vouchers and the meetings with member of the clinic social work team would allow participants to remain stably housed after the study ends. There is a possibility that the \$650 housing voucher would not be enough to obtain temporary housing for the participants. The member of the clinic social work team could address this situation by helping the participants obtain sources of income such as benefits for which the participant might be eligible or helping the participant find employment. Participants might also have other sources of income through employment or government benefits that could supplement the \$650 housing vouchers. Once the housing vouchers end, the next six months of meetings with the member of the clinic social work team would be dedicated to maintaining housing and obtaining permanent housing for the participants. If study participants are not housed by the end of the study or if they become homeless long after the study ends, then the participants would still have access to the social work assistance available to all patients at the ATP. This assistance can help connect patients at the ATP to housing resources, obtain benefits for which they are eligible, find temporary housing, or apply for permanent housing vouchers.

The principal Investigator will conduct a chart review of the methadone doses that participants receive in the 3-month period before the study, between Months 3 and 6 of the study, and between Months 9 and 12 of the study. The review of methadone doses will calculate the number of doses participants received and took home with them instead of receiving at the clinic. In addition to a review of methadone doses, the principal investigator will document results of the urine toxicology tests for the participants in the 3-month period before the start of the study and monthly during the study. Participants will complete two surveys at Day 0, Month 6, and Month 12 of the study: the OUD Checklist, which rates opioid use disorder symptoms based on the DSM-5 criteria, and the SF-36, which measures quality of life. At Months 6 and 12, participants will complete qualitative interviews to determine how the vouchers and social work assistance impacted their financial and social well-being, and whether the SASH Intervention was useful in combating homelessness. Data on the methadone doses, urine toxicology tests, surveys, and qualitative interviews will be stored in a password-protected database.

The principal investigator will calculate the percentage of days participants are homeless during the 6-month period when vouchers are distributed and at Month 12 of the study. The percentage of days participants are homeless will be calculated from data collected by the member of the clinic social work team. These data will be stored in a password-protected database. If there are concerns for the well-being of any of the participants in the study, including if a participant expresses thoughts to harm their self or others, then the principal Investigator [name], a board-certified psychiatrist, will be notified to address the situation. If there are medical concerns, one of the study Investigators [name], a Family Medicine physician, will be notified to address the situation. If the situation involves a potentially life-threatening emergency, then the participant will be sent to the Emergency Department.

2 * Describe all procedures already being performed for diagnostic or treatment purposes (If not applicable to the study, enter "N/A"):

All the participants will be currently receiving methadone for opioid use disorder treatment at the Addiction Treatment Program.

3 * Describe the duration of an individual participant's participation in the study:
Participants will participate in the study for 12 months.

4 * Describe the amount of time it will take to complete the entire study:
The study will take 15 months to complete the study and data analysis.

5 * Describe any additional participant requirements:

Participants will be recruited for the study if they are receiving methadone from the Addiction Treatment Center at the University of Maryland and are struggling with homelessness, which will be defined as living in an emergency shelter or a place not meant for habitation instead of a fixed, regular, and adequate nighttime residence for at least 15 of the 30 days preceding the first month of the study.

HP-00100771

Sample Size and Data Analysis_V2

Sample Size and Data Analysis

If you uploaded a separate research protocol document in the 'Research Protocol' page, cite the applicable section and page numbers from that document in the answer boxes below.

- 1 * Provide the rationale and sample size calculations for the proposed target population:
The study will recruit eight participants. This is a feasibility study, so the results will be used as pilot data to apply for a larger grant.
- 2 * Provide the plan for data analysis. Include in the description the types of comparisons that are planned (e.g., comparison of means, comparison of proportions, regressions, analysis of variance, etc.), which is the primary comparison/analysis, and how the analyses proposed will relate to the primary purposes of the study:
All the participants in this study will receive the intervention. The participants will not be compared with a matched control group. Comparisons of the percentages of missed and take-home methadone doses will be completed in the 3-month period before the study, between Months 3 and 6 of the study, and between Months 9 and 12 of the study. Comparisons will be completed of the results of the urine toxicology tests in the 3-month period before the start of the study and each month during the study. Comparisons will be completed for the OUD Checklist and SF-36 scores at each of the three time points. The analyses will determine how the study interventions impacted outcomes for opioid use disorder treatment, quality of life, and housing.

ID: VIEW4E02000052800
Name: v2_Sample Size and Data Analysis

HP-00100771

Sharing of Results_V2

Sharing of Results

1 * Describe whether results (study results or individual subject results, such as results of investigational diagnostic tests, genetic tests, or incidental findings) will be shared with subjects or others (e.g., the subject's primary care physicians) and if so, describe how it will be shared:
The results will not be shared with either the participants or anyone not involved in the study. The results would be written in a manuscript, but none of the participants would be identifiable by name, and all the data would be de-identified.

ID: VIEW/E02008C9D800
Name: v2_Sharing of Results

HP-00100771

Behavioral Methods and Procedures_V2

Psychological/Behavioral/Educational Methods & Procedures

You indicated on the "Type of Research" page that your study involves a psychological/behavioral/educational method or procedure such as a survey, questionnaire, interview, or focus group.

1 * Select all behavioral methods and procedures which apply to this study:

- Surveys/questionnaires
- Key informant or semi-structured individual interviews
- Focus groups or semi-structured group discussions
- Audio or video recording/photographing
- Educational tests or normal educational practices (education instructional strategies, techniques, curricula, or classroom management methods)
- Individual or group behavioral observations
- Psychosocial or behavioral Interventions
- Neuropsychological or psychophysiological testing
- Deception
- Other psychosocial or behavioral procedures

ID: VIEWIE09416F57600

Name: v2_Psychological/Behavioral/Educational Methods and Procedures

HP-00100771

Surveys/Questionnaires_V2

Surveys/Questionnaires

You indicated that this study involves surveys and/or questionnaires.

If you uploaded a separate research protocol document in the 'Research Protocol' page, cite the applicable section and page numbers from that document in the answer boxes below.

1 * List all questionnaires/surveys to be used in the study, including both standardized and non-standardized assessments:
 OUD Checklist Score
 SF-36
 Homeless Days Review Form

2 * Upload a copy of all questionnaires/surveys:

Name	Created	Modified Date
Homeless Days Review Form(0.01)	7/6/2022 10:39 AM	7/6/2022 10:39 AM
SF-36 Form.pdf(0.01)	5/2/2022 10:02 AM	5/2/2022 10:02 AM
OUD Checklist.pdf(0.01)	5/2/2022 10:02 AM	5/2/2022 10:02 AM

3 * What is the total length of time that each survey is expected to take?
 The OUD Checklist will take 10 minutes, the SF-36 will take 15 minutes, and the Homeless Days Review Form will take 10 minutes..

4 * Are any of the questions likely to cause discomfort in participants or cause harm if their confidentiality were breached? (i.e., Illegal activities)
 Yes No

5 * Do any questions elicit information related to the potential for harm to self or others?
 Yes No

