During these meetings, the member of the clinic social work team would conduct a needs assessment on the participant to determine barriers to the participant's receiving and remaining in stable housing. The social work assistance provided at these meetings would be more intensive than what is usually provided at the ATP, and the assistance would be individualized to the needs of the participants. A member of the clinic social work team would help participants obtain sources of income by obtaining government benefits for which the participants are eligible or helping the participants gain employment. They would address issues placing the participants at risk for losing their housing such as disputes with their landlords or difficulties budgeting finances. They would also help the participants apply for permanent housing vouchers from the city of Baltimore so that the participants are housed once the study ends. The meetings will be scheduled at least monthly, but participants will be encouraged to schedule these more frequently.

A member of the clinic social work team would administer the surveys documenting the percent of days participants are homeless. A member of the clinic social work team could keep written notes for supervision or treatment purposes, but no other written documentation from these meetings would be kept for study or research purposes. The results of the surveys would be uploaded to a password-protected electronic database. After the results of these surveys are uploaded to the password-protected database, any written documentation of these surveys will be discarded in receptacles designated for destroying documents with patient-health information. Written documentation for the member of the clinic social work team would not contain any information identifying the participants to ensure confidentiality. Any written documentation needed by the member of the clinic social work team that contained information identifying the participants would be kept at the ATP in a locked cabinet accessible only to staff associated with the study.

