The greatest risk to participants in this study is a breach in confidentiality, which would cause minimal harm if this did occur because the data collected in this study would not risk the legal or health status of the study participants. The potential benefits of the study are improvements in opioid use disorder and methadone treatment, quality of life, and housing. These potential benefits greatly outweigh the study's low potential risk of harm.
- 4 * Describe the alternatives to participation in this study. If there are no alternatives, state that participation is voluntary and the alternative is not to participate. For Intervention studies, describe appropriate alternative clinical procedures or courses of treatment available to subjects.
Participation in this study is voluntary, so the alternative is not to participate in the study.

ID: VIEW4E1B6281B0400
Name: v2_Potential Benefits and Alternatives

HP-00100771

Withdrawal of Participants_V2

Withdrawal of Participants

If the questions below are not applicable to the research (i.e., chart review), enter "N/A".

- 1 * Describe anticipated circumstances under which subjects will be withdrawn from the research without their agreement:
Participants could be withdrawn if the study Investigators do not believe that continuing in the study is in the participant's best interest, if they miss more than 50 percent of the monthly meetings with members of the clinic social work team, enter substance use treatment that is associated with housing, or discontinue their methadone treatment at the Addiction Treatment Program.
- 2 * Describe procedures for orderly termination:

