Study Investigators would try to engage participants who do not attend meetings with members of the clinic social work team. If participants continue to miss meetings or if continuing in the study would not be in the best interest of the participant, then study investigators would contact the participant to explain the reason for their termination from the study. The study investigators would explain to the participant that their removal from the study would not affect the care they receive at the Addiction Treatment Program (ATP), and the participant would be given the opportunity to ask questions about their removal from the study. If the participant is in temporary housing paid for by the housing vouchers, or if the study had been helping the participant apply for government benefits, gain employment, or apply for permanent-housing vouchers, then staff from the study would update the social workers at the ATP and help transition the participant to the social work assistance available to all patients at the ATP. The goal of doing this would be to give the participant the best opportunity to remain housed and continue the work started during the study.
- 3 * Describe procedures that will be followed when subjects withdraw from the research, including partial withdrawal from procedures with continued data collection:
Data from the participants removed from the study would be included in the data analysis. Any termination or withdrawal from the study would be noted in the manuscript documenting the results of the study. The care participants receive for their opioid use disorder would not be affected by their withdrawal from the study.

ID: VIEWE1B82531F800
Name: v2_Withdrawal of Participants

HP-00100771

Privacy of Participants_V2

Privacy of Participants

If the study does not involve interaction with participants, answer "N/A" to the questions below.

- 1 * Describe how you will ensure the privacy of potential participants throughout the study (**privacy refers to persons and their interest in controlling access to themselves**):

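### Does the plan contradict itself on whether missing more than half of the social work meetings ends participation?

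*Combined protocol and SAP*

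**What the plan says.** Study Procedures, item 1, gives the attendance rule in definite terms: "participants will be removed from the study if they miss more than 50 percent of scheduled meetings".

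Withdrawal of Participants, item 1, answers a form question about when subjects will be taken out of the research without their agreement. The answer begins "Participants could be withdrawn if the study Investigators do not believe" that staying in is best for the participant. It then adds three more circumstances. One is attendance: "if they miss more than 50 percent of the monthly meetings with members of the clinic social work team". The others are entering substance use treatment linked to housing, and stopping methadone at the Addiction Treatment Program (ATP).

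On frequency, Study Procedures says "The participants will meet with the member of the clinic social work team at least once a month for twelve months", and Behavioral Intervention, item 1, says "The meetings will be scheduled at least monthly, but participants will be encouraged to schedule these more frequently". The latter section also limits the research record. Apart from the surveys of homeless days and any notes for supervision or treatment, "no other written documentation from these meetings would be kept for study or research purposes".

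Withdrawal of Participants, item 2, describes the steps around termination. First, "Study Investigators would try to engage participants who do not attend meetings with members of the clinic social work team". If absences go on, the investigators explain the reason for termination, and staff "help transition the participant to the social work assistance available to all patients at the ATP". Item 3 keeps removed participants' data in the analysis and has terminations and withdrawals noted in the manuscript.

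**The concern.** One sentence says removal happens at the threshold; the other says it may. Two participants with the same attendance could be handled differently, each in line with one section. The rule decides whether a homeless participant keeps the study's more intensive support or moves to the help open to all ATP patients. It also sets the termination count in a study of eight whose results are meant as pilot data.

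Three smaller points add to the doubt. One section counts scheduled meetings and the other monthly ones. Neither says over what period the 50 percent is reckoned. The engagement step is not tied to the threshold. Since little meeting documentation is kept for research, one might also ask how attendance would be established.

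**Working it through.** The plan has no figure to reproduce. The check compares the texts and adds simple arithmetic for scale.

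**Inputs.** At least one meeting a month for 12 months, so at least 12 meetings (Study Procedures, item 1). Eight participants (Sample Size and Data Analysis, item 1). Threshold: more than 50 percent missed (both sections).

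**1. Who is affected.** Take exactly 12 meetings, the stated minimum. Missing 6 gives 6/12 = 50.0%, which is not more than 50 percent, so neither sentence applies. Missing 7 gives 7/12 = 58.3%, so both apply. The wording differs only for participants missing 7 to 12.

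**2. Are the two sentences incompatible?**

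| Action for a participant over the threshold | Study Procedures, item 1 | Withdrawal of Participants, item 1 |
|---|---|---|
| Removed | consistent | consistent |
| Kept | not consistent | consistent on a literal reading |

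One course of action satisfies both texts, so they can be followed together. The literal reading of the second is also not the only one. Its verb governs four unlike circumstances, the first of which is a judgement by the investigators, and it answers a question framed as when subjects *will* be withdrawn. In that setting it can simply mean that these are the ways withdrawal may come about. This is not proof of what was intended, but it weakens the claim that two different rules were meant.

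**3. The engagement step.** Item 2 of the withdrawal section answers a question about orderly termination. Contacting non-attenders before ending participation fits either reading. It does not restate the percentage, so it neither settles nor deepens the difference.

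**4. Scheduled or monthly meetings.** The design section, Study Procedures and Behavioral Intervention all describe a single series held at least monthly. No separate class of monthly meetings, as opposed to extra ones, is defined. The two phrases give different denominators only if such a class is assumed.

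**5. Counting period.** This is a true omission. Missing 4 of the first 6 meetings and none of the next 6 is 4/6 = 66.7% at Month 6 and 4/12 = 33.3% at Month 12. It bears on how the rule is run, and it would remain if the verbs were aligned.

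**6. What reaches the analysis.** Sample Size and Data Analysis, item 2, plans comparisons over time of missed and take-home methadone doses, urine toxicology, the OUD Checklist and the SF-36. It names no retention endpoint, progression criterion or formal test that a removal count would feed. Removed participants stay in the analysis and terminations are reported. Each removal is 1/8 = 12.5% of those enrolled.

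**7. Knowing attendance.** Voucher use already requires attendance, and the social work team may keep notes for supervision or treatment. The team therefore has to know who attended, at least during the six voucher months, even though no research log is specified.

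**The case for a change.** The strongest case against this view concerns Months 7 to 12. Vouchers stop after six months while meetings run for twelve, so in the second half removal is the only stated consequence of not attending. The best-interest judgement in the same list, and the engagement step, both fit discretion better than automatic removal, so the form's question does not settle the matter. In a study of eight, one removal is 12.5% of the sample, and a reader cannot interpret the termination count without knowing the rule behind it. The documents also do not say whether data collection continues after removal, although the form asks.

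Much of this is fair. The wording does differ, and no section says which governs. What does not follow is harm to the results. Every termination is to be reported, and stating the reason and the rule applied is ordinary reporting. Later data could be missing if collection ended at removal. That would follow from any removal under either verb, and the documents do not say that it ends. Candidates are also chosen partly for their likely attendance (Recruitment, item 1), so few may cross the threshold, though no expected number is given.

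**Conclusion.** The difference between the two sentences is genuine but clerical. Around it are small gaps (counting period, link to the engagement step, collection after removal) that a study team can fill sensibly as it goes. No effect on any planned comparison is shown. This is a single-arm feasibility study of eight people with no retention endpoint and no formal test, it keeps removed participants' data, and it reports terminations.

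This rests on two assumptions: that those commitments in Withdrawal of Participants, item 3, are honoured, and that the team can tell who was removed and why. The sentences in Study Procedures and Withdrawal of Participants should be reconciled when the application is next edited, with the choice of rule left to the investigators. That is tidying, and neither the design nor the analysis needs to change because of it.
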